3. BACKGROUND, RATIONALE, AND OBJECTIVE

[figure not shown]
a. Background

To achieve global goals for the treatment of HIV, most high-prevalence countries are experimenting with and scaling up differentiated service delivery models (DSD). To date most of these efforts have focused on "stable" antiretroviral therapy (ART) patients, who have passed the period of high mortality and loss-to-follow-up immediately after initiating ART. Stable patients are believed to require fewer provider resources (e.g. clinical consultations) and are able to benefit from community-based service delivery that is closer to home[1] and from less intensive clinic visits. A handful of efforts have been formally described and evaluated in the literature[2–6]; many others are being implemented formally or informally under routine care, without a research or evaluation goal. While there is currently no reliable count of how many ART patients are participating in alternative service delivery approaches, it is likely that nearly every major HIV treatment partner supported by PEPFAR and the Global Fund have introduced one or more alternative models of care into the programs they support.

At present, some studies have reported outcomes for specific models of care and/or compared one model to another, and several large studies are currently underway to evaluate individual models. For most countries, though, we have little evidence on overall impact. We cannot currently estimate basic aggregate descriptive measures such as the proportion of clinics offering alternative models, the proportion of patients considered eligible or the number of patients actually participating. Nor do we know eligibility criteria for each model in each country, empirical resource utilization compared to traditional care, or core outcomes such as viral suppression. We have almost no data on variations among the models, duration of patient participation, fidelity to model guidelines, effects on clinic efficiency, and sustainability without external donor support. Many efforts are underway to improve use of alternative models, but their focus is on implementation rather than high-level evaluation or analysis of the phenomenon as a whole.

For purposes of this protocol, we will refer to any approach to service delivery that is tailored to some aspect of patient needs as a "differentiated service delivery model," or DSD. The original model of clinic-

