based ART provision for all patients will be called the "conventional" model and will be considered a single model of care. All other models of care will collective be called "alternative" models. A health system that optimizes the provision of approaches will offer one or more alternative models of care for all ART patient populations,

stratified on the basis of criteria ranging from setting (e.g. rural v urban) to risk factors (MSM v young women), patient characteristics (age, sex, condition), to clinic capacity. In this taxonomy, the conventional model of care may serve a specific group of patients—those who require additional services—and it is thus a differentiated model in itself.

In Malawi, the Ministry of Health (MOH) and its implementing partners are currently supporting the scale-up of several alternative models of care ART patients who are stable on ART. These include amongst others, multi month dispensing, fast track refills, nurse led community ART and adolescent centric treatment groups. While some specific DSD models have been or are being evaluated[7-10], there has not yet been an assessment of the reach or impact of DSD at national scale.

b. Rationale

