In the published literature and conference presentations, calls for funding proposals, and MOH documents, DSD are assumed to generate a wide range of potential benefits. These include better access to and outcomes of treatment, increased clinic capacity and lower costs for providers, lower costs for patients, and better quality and greater satisfaction for both providers and patients. Despite a high level of confidence on the part of DSD advocates, ministries of health, funders, and implementing partners that at least some of these benefits must materialize, there is in fact very little evidence to support these assumptions. Published research to date has suggested modest or minimal improvement in health outcomes and small reductions (if any) in per-patient provider costs. We note that there is little room for short-term improvement in health outcomes, as most patients enrolled in alternative models to date have been virally suppressed at entry, but DSD may certainly affect long-term retention in care. We also expect only modest potential for per-patient out-of-pocket cost reductions, due in part to the large share of costs attributable to medications[11-13]. We have found no published evidence that moving HIV patients into alternative models increases the quality or quantity of services that clinics provide to conventional-model patients or patients with non-HIV conditions.

Fortunately, in the past half-decade, substantial groundwork has been laid for standardizing methods for evaluating the performance of DSD at the patient level. We are thus at a point in time at which many alternative models are already being implemented and some evaluated, and an initial set of evaluation indicators has been published[14]. With some micro-data in hand, but little "macro" evidence of overall scale, impact, costs, and benefits, this is therefore an apt time to launch a big picture analysis of DSD, to help guide ministries of health, donor agencies, and others to make better decisions about what to scale up, where, and for whom.

c. Objective

The objective of this study is to analyze existing data sets with data relevant to differentiated service delivery for HIV treatment in Zambia, Malawi, and South Africa. This protocol is solely for the analysis of existing data; the study contains no interaction with patients, providers, or other individuals.

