- Date ART initiated (first dose of medications dispensed)
- First-line regimen prescribed
- Any changes to first line regimens and dates of changes
- Dates, quantity (duration), and type for all medication collections
- Dates and results of all viral load tests
- Dates and results of all other laboratory investigations

DSD information

- Model(s) of care enrolled in and duration of enrollment
- Eligibility criteria and dates for alternative model of care
- Dates of participation in DSD activities (e.g. adherence club attendance, CCMDD pickups, multimonth dispensing, etc.)
- Other resources used for ART and recorded in the data source

In addition, we will collect aggregate, clinic- or DSD-level information about resources utilized, providers accessed, volumes served, etc. **This will not be human subjects research.** We will obtain this information from descriptions included in papers and reports, and, where necessary, surveys conducted by the study team.

c. Data Entry and Storage

The data sets that will be analyzed in this study will be shared with the study team by the Ministry of Health, implementing partners, or other researchers/evaluators. For all patient data extracted from paper files and registers, we anticipate entering all data onto electronic case report forms on tablets on site, so that paper forms do not need to be removed from the study clinics. Once patient information is captured on the tablet, the information will be immediately sent to a highly secure cloud server and wiped from the tablet. Once the databases are received by the study team, the data will be downloaded onto secure, protected drives at the HE²RO office in South Africa and at Boston University, with access limited to relevant study staff. Details on data transfer and drive security are provided under Subject Confidentiality below.

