Outcomes 9-11 measure health outcomes by model of care. For these outcomes, we will begin with descriptive analyses of the characteristics of the population stratified by model of care. For each outcome described above, we will conduct a crude analysis comparing the proportion of subjects with the outcome by model of care. Next, we will conduct an analysis for each outcome accounting only for clustering using generalized estimating equations (GEE) with an unstructured correlation matrix and clustering by treatment site. In all cases the outcomes are dichotomous and therefore we will calculate risk differences comparing the intervention to the comparison arms using a linear link function and a binomial distribution. Next, should any imbalances between models of care be detected, we will adjust for those covariates in our GEE model. Finally, we will look for differences in the effects of the models of care by important baseline characteristics (e.g. size of the treatment population, rural vs. urban, province, etc.) using stratified analyses.

d. Dissemination of Findings

The results of this study will be disseminated as widely as possible in the study countries and globally. A full report will be made to local stakeholders and will be circulated widely and posted on our website. We will also develop a short briefing document to send to the Ministry of Health, donor agencies, and other interested organizations, and we will present the results at relevant conferences domestically and internationally. One or more journal manuscripts will be submitted to an appropriate peer-reviewed international journal.

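### Retention and viral suppression are compared by model of care with no eligibility restriction and adjusted only for detected imbalances, so selection is expected to appear, at least in part, as a DSD benefit

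*Protocol*

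**What the plan says.** **Who enters which model.** Section 3a of the protocol says most DSD efforts so far concern stable patients, "who have passed the period of high mortality and loss-to-follow-up immediately after initiating ART", and that Malawi is "supporting the scale-up of several alternative models of care ART patients who are stable on ART". Section 3b adds that "most patients enrolled in alternative models to date have been virally suppressed at entry". Section 3a treats conventional care as one model and says that "the conventional model of care may serve a specific group of patients", namely those who need additional services.

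**Who is analysed.** Section 5b includes everyone aged 15 or older in HIV care during the data period and lists no exclusions.

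**How health outcomes are compared.** For Outcomes 9-11, Section 7c states that "we will conduct a crude analysis comparing the proportion of subjects with the outcome by model of care". A GEE model follows that allows for site clustering without covariates, giving risk differences "comparing the intervention to the comparison arms using a linear link function and a binomial distribution". The last step before the stratified analyses is the rule that "should any imbalances between models of care be detected, we will adjust for those covariates in our GEE model".

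**What is available.** Section 6b lists "Eligibility criteria and dates for alternative model of care" among the fields to be collected. Section 7c uses an eligibility classification for Outcomes 1-4 but does not carry it into Outcomes 9-11.

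**The concern.** Entry to an alternative model depends largely on having stayed in care and being suppressed, and these are the two health outcomes being compared. Patients who have just started ART, or who are unstable, fall into the conventional group by default. A difference between the groups can then arise from who was admitted, with no contribution from the model of care.

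The adjustment rule is a weak safeguard. Whether an imbalance is detected depends on the number of records and on the test used. It does not show whether a covariate is a confounder. The rule also does not say that covariates must be measured before model entry.

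The bias would run in favour of DSD on both outcomes, and more records would not reduce it. The stated purpose is to evaluate the outcomes and benefits of DSD and to inform national decisions.

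**Working it through.** The protocol states no effect size, outcome rate or power for this comparison, so there is no figure to reproduce. The 1,000,000 in Section 7a is a population count. All rates below are assumptions.

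**1. Crude and cluster-only comparison when DSD has no effect.** Let *f* be the share of conventional patients who are ineligible, and *R_e* and *R_i* the 12-month retention of eligible and ineligible patients. If all alternative-model patients are eligible:

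RD = *R_e* − [(1 − *f*)*R_e* + *f* *R_i*] = *f*(*R_e* − *R_i*)

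| *f* | *R_e* | *R_i* | Spurious RD |
|---|---|---|---|
| 0.20 | 0.93 | 0.85 | 0.20 × 0.08 = +1.6 points |
| 0.50 | 0.95 | 0.80 | 0.50 × 0.15 = +7.5 points |
| 0.50 | 0.95 | 0.70 | 0.50 × 0.25 = +12.5 points |

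Allowing for clustering alone leaves this about the same if the patient mix is similar across sites.

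**2. Imperfect enforcement of eligibility.** More generally, RD = (stable share in DSD − stable share in conventional) × (rate in stable − rate in others). With rates of 95% and 75% and a conventional group that is 50% stable, an entirely stable DSD group gives (1.0 − 0.5) × 0.20 = +10 points. A DSD group that is 90% stable gives (0.9 − 0.5) × 0.20 = +8 points. The bias does not need complete separation of the groups.

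**3. Adjusted comparison.** This was illustrated by one simulation of 1,000,000 patients with a true effect of zero. An unmeasured stability trait influenced age, time on ART, prior suppression, uptake among eligible patients and the outcome. Eligibility required a minimum time on ART and a suppressed prior viral load. Risk differences came from linear regression without clustering.

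| Analysis | RD (points) |
|---|---|
| Crude, all patients | +6.9 |
| Adjusted for age and time on ART | +6.1 |
| Prior viral load added | +3.3 |
| Eligible patients only, unadjusted | +3.3 |
| Eligible only, adjusted for age and time on ART | +3.0 |

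The result depends heavily on whether prior viral load enters. The simulation gave every patient a prior viral load, whereas Section 6b says new initiators will have none.

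**4. What detection would mean at this size.** If it meant a two-sided 5% test with 80% power and equal unclustered groups, the smallest detectable standardised difference is (1.96 + 0.84) × √(2/*n*) with *n* per group:

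- 1,000,000 records: 2.80 × √(2/500,000) = 0.0056
- 740,000 records: 2.80 × √(2/370,000) = 0.0065

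Almost every recorded covariate would be flagged, whether or not it confounds. The protocol names no test or threshold, so this is one reading of the rule.

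**The case against.** **The comparator is inferred.** Section 7c refers only to comparison arms, Section 7b allows stratification by patient characteristics, and a separate analysis plan could restrict the population. It stands that the all-patient comparator is an inference. It follows, however, from comparison by model of care, a single conventional model and no exclusions. The population, the contrast and the adjustment rule are written in the protocol itself.

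**The study is descriptive.** That statement in Section 7c belongs to Outcomes 1-4. The text on Outcomes 9-11 speaks of an intervention and of differences in the models' effects.

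**With so many records, the real confounders would be flagged and adjusted for.** This stands in part. Including prior viral load and time on ART would reduce the bias. The rule does not secure it, and new initiators have no value to adjust for.

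**Positivity.** A reader might infer that ineligible patients could never have entered an alternative model, so that regression cannot help at all. The documents do not support this. Section 3a says most efforts, not all, concern stable patients, and says only that conventional care may serve a particular group. In the simulation, adjustment including viral load did as well as restriction (+3.3 points each).

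**Post-entry covariates.** A reader might infer that visit counts or refill length will be adjusted for. Section 7c does not say so; it only fails to exclude them.

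**Conclusion.** The concern holds in a bounded form. Under Section 7c as written, selection into alternative models is expected to contribute to the risk differences for Outcomes 9-10, in favour of DSD. The +1.6 to +12.5 points apply to the crude and cluster-only estimates, with no true effect and the assumed rates above. They do not describe the adjusted estimate. That estimate's bias depends on which covariates the rule admits, and it was +3.3 to +6.1 points across the all-patient adjusted analyses in the simulation.

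Two stronger conclusions are not supported. The documents do not show that the estimates would measure mainly selection, because no actual rates or eligibility shares are given. Nor does the protocol itself forecast small true effects: Section 3b reports that published studies have found little improvement, and adds that long-term retention may be affected.

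**What to change.** For Outcomes 9-10 in Section 7c:

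- Make the effect comparison among patients who meet the alternative-model eligibility criteria at a common index date, in both groups. Use the enrolment date for alternative-model patients, and a matched calendar date or eligible visit for those remaining in the conventional model.
- Replace the imbalance rule with a fixed set of confounders measured at or before the index date, included whatever the observed imbalance: age, sex, time on ART, last viral load, baseline CD4 and WHO stage, regimen, and calendar period.
- Keep the all-patient comparison as description, without effect language.

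**Cost.** The change needs new analysis wording and derivation from fields already planned in Section 6b. The conventional group shrinks by the ineligible share, which is 20-50% under the assumptions above. In the simulation, with 75.3% eligible and 39.2% in DSD, it falls from 608,000 (1,000,000 − 392,000) to 361,000 (753,000 − 392,000). There would be no effect estimate for ineligible patients. The analysis would depend on how completely eligibility and model of care are recorded. Section 6a says the national electronic system does not fully capture the model, so paper files may be needed. Selection among eligible patients would remain (+3.0 points in the simulation) and should be stated as a limitation.

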7. DATA ANALYSIS

a. Sample Size

In order to measure national coverage of DSD, we will access data for up to the entire national ART cohort. In Malawi, the estimated number of individuals on ART is currently 740,000 [16]. This is expected to increase to \geq 90% of the entire HIV-infected population by the time the study ends. We therefore expect to collect and analyze data for up to 1,000,000 individuals, the estimated HIV-positive population in Malawi [16]. As noted above, all data will be drawn from records that exist at the time of data collection; the study will have no interaction with study subjects.

b. Outcomes

To estimate uptake, benefits, and costs of DSD, we will aim to report the following results, stratified by model care and/or other patient or clinic/model characteristics:

- Percentage of current ART patients eligible for any alternative model, under current guidelines
- 2. Demographic, economic, and clinical characteristics of patients in each model, as data allow.
- 3. Patient-months enrolled in any DSD and in each model
- 4. Frequency of transfer between models of care, including back to the conventional model
- 5. Location, duration, and frequency of ARV dispensing
- 6. Number of clinical visits/patient/year
- 7. Quantities of resources used/patient/year
- 8. Geographic distribution of patients enrolled in each DSD
- 9. Retention on ART, measured at 6-month intervals
- 10. Proportion virally suppressed (< 400 copies/ml³)
- 11. Other outcomes relevant to DSD that can be estimated from available data

Note: as this is not a clinical trial, we have not designated primary and secondary outcomes. We will report as many of the above outcomes as data allow.

c. Analysis

To evaluate the broad, national- or system-wide implications of differentiated models of ART delivery in the context of health systems in sub-Saharan Africa, we will conduct the following analyses.

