Outcomes 1-4 above entail description of the models of care and the patients enrolled in them. For these outcomes, we will begin by categorizing patients in the sample as to whether they are eligible for and receiving one of the models of care and report the proportion in each group. We will then describe the demographic, economic, and clinical characteristics of patients stratified by model of care (age, gender, time on ART, baseline CD4, and others) using means or medians as appropriate for continuous variables and proportions for categorical variables. We will further quantify the number of patientmonths enrolled in any DSD model and in each specific model and the frequency of transfer between models of care, including back to the conventional model. We will look for differences in the models of care, number of patient-months enrolled, and frequency of transfer by demographic, economic, and clinical characteristics using stratified analyses and report risk differences and corresponding 95% confidence intervals. As the analysis is meant to be descriptive we will not conduct regression analyses as our primary analyses.

Outcomes 5-6 describe characteristics of the models of care that are being implemented. Separately from this protocol, we will review governmental and implementing partner SOPs, reports, and manuscripts in order to describe features of the models of care including location, duration, frequency

of ARV dispensing, and the number of clinical visits per patient per year (all non-human subjects research). We will report these using means or medians as appropriate for continuous variables and proportions for categorical variables. We will then compare the expected features to patient data and report the proportion of agreement to determine whether the models of care are being implemented as per SOP. We will present these as proportions with corresponding 95% confidence intervals.

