The indirect benefits of this study are expected to be large. Differentiated service delivery models are being scaled up across sub-Saharan Africa and will ultimately affect hundreds of thousands, if not millions, of patients. Generating information about coverage, allocation, costs and benefits of these programs has the potential to make the DSD models more effective nationwide. The evaluation will also assist the MOH to target and tailor its interventions and allocate its resources to the patients at greatest need and/or most likely to benefit and help project budgetary needs in future years.

e. Risk to Benefit Ratio

Because the indirect benefits of the study are large and the risks to human subjects are minimal, we are confident that the risks to subjects are reasonable in relation to anticipated benefits.

f. Recruitment Procedures

As explained above, we will not generate any new (not yet collected) data for this study, nor will we have any interaction with study subjects. We will therefore not have an active recruitment procedure. We will enroll in the study all current and former ART patients accessing HIV care from January 1, 2014 to February 28, 2021. No screening of study subjects will be conducted.

g. Informed Consent

We do not intend to seek informed consent for this study which is a retrospective record review only and poses minimal risk to study subjects. We therefore request a Waiver of Informed Consent.

h. Subject Confidentiality

As explained above, we will take multiple steps to protect subject confidentiality. These are detailed in the paragraph entitled "Potential Risks and Protections."

i. Destruction of Identifiers

The linking files will be kept until all data collection for each individual study subject is complete, the data set has been closed, and all data has been linked. Once the linking is complete, the linking file will be destroyed. All data collection files will be coded using patient ID numbers and not contain subject identifiers. We note that some data sets, such as those from completed trials, will be closed (no further updates expected) when we receive them, and these data can be de-linked soon after receipt. Other data sets, like longitudinal electronic medical record data, will not be closed until the study is completed, as we anticipate receiving updated EMR data sets periodically throughout the project.

j. Costs and Payments

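### For Outcomes 9-11 the protocol seeks differences in model effects between kinds of site but plans only stratum-by-stratum estimates, with no estimate or interval for the difference itself

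*Protocol*

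**What the plan says.** Protocol section 7c sets out a sequence for Outcomes 9-11 (retention, viral suppression and other outcomes relevant to DSD). A crude comparison by model of care comes first. Next comes "generalized estimating equations (GEE) with an unstructured correlation matrix and clustering by treatment site", from which "we will calculate risk differences comparing the intervention to the comparison arms using a linear link function and a binomial distribution". Covariates are then added if the models of care are imbalanced. In the last step "we will look for differences in the effects of the models of care by important baseline characteristics". The examples are "e.g. size of the treatment population, rural vs. urban, province, etc", and the method is given at the end of the same sentence: "rural vs. urban, province, etc.) using stratified analyses".

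The protocol nowhere mentions an interaction term, a test of homogeneity or a contrast between strata. It also gives no rule for when stratum results count as different. For Outcomes 1-4, section 7c pairs stratified analyses with an instruction to "report risk differences and corresponding 95% confidence intervals". The paragraph on Outcomes 9-11 states no confidence level. Section 7c's remark that regression is not the primary analysis belongs to Outcomes 1-4; Outcomes 9-11 are analysed by regression.

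**The concern.** The stated aim is effect modification: whether a model of care does better in one kind of site than in another. The target is a difference between two risk differences. Estimating each risk difference separately does not report that target, so the reader must compare strata by eye, usually by asking which are significant or whether their intervals overlap.

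These results have a use. Section 3b wants the analysis to inform decisions on what to expand, in which places and for which patients. Section 8d expects it to help the ministry "target and tailor its interventions and allocate its resources to the patients at greatest need", and section 7d promises a short briefing for the ministry and donors. Site size, rural or urban setting and province are the characteristics on which such targeting would rest. A mistaken reading of the strata could therefore become a statement that a model works in one setting and not in another, or could hide a real difference.

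**Working it through.** **Inputs.** The protocol gives no alpha, power or error rate for this step, so there is no figure of its own to reproduce. Assumed here: two-sided 0.05, independent strata, the same true effect in every stratum, and power p within each stratum over a range.

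**1. Comparing significance across strata.** With two strata, the chance that exactly one is significant is 2p(1-p). With K strata, the chance that they do not all agree is 1 - p^K - (1-p)^K.

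| Power per stratum | 2 strata | 3 strata | 5 strata |
|---|---|---|---|
| 20% | 32% | 48% | 67% |
| 30% | 42% | 63% | 83% |
| 50% | 50% | 75% | 94% |
| 80% | 32% | 48% | 67% |
| 95% | 9.5% | 14% | 23% |
| 99% | 2% | 3% | 5% |

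For two strata the rate stays above 5% until power per stratum passes about 97.4%, the upper root of 2p(1-p) = 0.05.

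Splitting a sample lowers power quickly. Overall power of 80% corresponds to an expected z of 1.96 + 0.84 = 2.80. In two equal halves each has 2.80/√2 = 1.98, so power is about 51% and disagreement 50%. In an 80:20 split the powers are 71% and 24%, and disagreement is 0.707 × 0.760 + 0.240 × 0.293 = 61%.

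**2. Dependence on size.** A simulation used an assumed 90% against 92% in both strata, no clustering and 100,000 runs per size:

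| Per arm per stratum | Power | One significant, one not | Direct contrast significant | 95% intervals do not overlap |
|---|---|---|---|---|
| 500 | 20% | 32% | 5.1% | 0.6% |
| 1,700 | 53% | 50% | 5.0% | 0.6% |
| 3,000 | 77% | 35% | 4.9% | 0.5% |
| 5,000 | 94% | 12% | 5.0% | 0.6% |
| 10,000 | 99.9% | 0.3% | 5.0% | 0.6% |

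The direct contrast holds its 5% level at every size.

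**3. Requiring non-overlap.** With equal standard errors, two 95% intervals separate only if the estimates differ by more than 2 × 1.96 × SE. The standard error of the difference is √2 × SE, so the threshold is z = 2 × 1.96/√2 = 2.77, or two-sided p = 0.0056. This rule errs the opposite way and misses real differences.

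**4. What the contrast shows.** Take 1,700 per arm per stratum under the same assumptions. SE = √[(0.90 × 0.10 + 0.92 × 0.08)/1,700] = 0.0098, a 95% half-width of 1.9 points. Suppose the strata give 2.5 points (0.6 to 4.4) and 1.5 points (-0.4 to 3.4). One is significant and the other is not. The difference is 1.0 point with half-width 1.96 × √2 × 0.0098 = 2.7 points, so the interval runs from -1.7 to 3.7. That does not establish a difference in effect.

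**5. How the contrast can be obtained.** The named characteristics belong to sites, so each site falls in one stratum. The stratum estimates are then independent and Var(D1 - D2) = SE1² + SE2². Subtraction is enough, and so is a joint model with model-by-characteristic terms.

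**The case against.** A reader might infer that the plan will often report differences that do not exist. The protocol does not support that. It states no significance comparison and no overlap rule for these outcomes, and the two rules err in opposite directions. The error rates describe what happens if a reader adopts one of them.

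Size also matters. Section 7a says "We therefore expect to collect and analyze data for up to 1,000,000 individuals"; if every stratum is that well filled, disagreement in significance almost vanishes. Against this, section 5a allows smaller partner or clinic cohorts, section 6a says the national system does not fully record model of care, and site clustering reduces the effective sample. Moderate power is plausible for some models but is not shown.

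A reader might also infer that separate stratum variances are less reliable than those of one joint model. For site-level characteristics this fails. The strata hold different sites, so the robust variance of each stratum effect in a joint model still rests on that stratum's own sites. Having few sites per stratum is a limit of the data that the fix does not remove. For the same reason stratification is not a wrong method, and the missing contrast can be computed from its output.

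Finally, a statistical analysis plan that is not shown might supply the contrast. That is possible, but the protocol itself names the method for this aim, and the method as named stops short of it. The weight is limited because section 7b designates no primary outcome and this step comes last.

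**Conclusion.** The concern holds as a gap in what is estimated and reported. The protocol sets out to find differences in effect and commits only to stratum-specific risk differences, with no contrast between them and no interval. If significance is compared across two strata, equal true effects look different in 32% to 50% of cases at 20% to 80% power per stratum, and more often with more strata; the rate is near zero when all strata are very large. If non-overlap is required, the effective level is about 0.6%. These figures assume two-sided 0.05, independent strata, equal true effects and, for the overlap figure, equal standard errors. The power range is an assumption, because the protocol gives none. The point is minor: a specific improvement to a stated method, not a flaw that undermines the study.

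**What to change.** Keep the stratum-specific estimates and extend the last step for Outcomes 9-11 in section 7c, for example: *For each characteristic we will also report the difference between the stratum-specific risk differences with its 95% confidence interval, from model-of-care by characteristic terms in the adjusted GEE. Where strata contain different sites, the estimates may instead be subtracted and their standard errors combined. Any statement that effects differ will rest on this contrast. These analyses are exploratory.*

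The subtraction route suits only site-level characteristics. If the open list of characteristics is extended to patient-level ones, a site can contribute to both strata and the joint model is needed.

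The cost is more than one term per characteristic. Section 3a names four alternative models as examples, beside the conventional one. Four model contrasts against a characteristic with L levels need 4 × (L - 1) terms: 4 for two levels and 8 for three. Intervals will be wide where strata contain few sites. Several contrasts still accumulate error (1 - 0.95³ = 14.3% for three independent tests, 1 - 0.95⁶ = 26.5% for six), which is the reason for the exploratory label. No new data are needed.
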